#### 1.2 **Purpose**

The purpose of this study is to determine whether potentiating the cystic fibrosis transmembrane conductance regulator (CFTR) with QBW251 in subjects with COPD will be efficacious with regards to reducing lung and systemic inflammation and bacterial colonization as potential drivers of airway obstruction, airway destruction, remodeling and exacerbations.

Furthermore, this study will provide supportive data to investigate the relationship of COPD CCI phenotype and the response in small airway structure, function and spirometry indices as well as in improvement of overall COPD symptoms and quality of life.

Commercially Confidential Information

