### 6.2.1.1 Permitted concomitant therapy requiring caution and/or action

Table 6-2 provides an overview of medications permitted under certain conditions, including bronchodilator medications which need to be withheld for certain timeframes prior to spirometry assessments on visit days, and an overview regarding actions to be taken for antibiotics.

Table 6-2 Medications permitted under certain conditions

Rationale/Group	Medication	Prohibition Period	Action Taken
COPD maintenance background therapy	e.g.Vilanterol, Umeclidinium, Indacaterol Glycopyrronium	Hold treatment for 24 hours (+/-2 hours) prior to each FEV 1 / spirometry measurement on visit days for once daily inhaled background therapy and 12 hours (+/-2 hours) for twice daily inhaled background therapy	In case the washout criterion is not fulfilled, reschedule spirometry accordingly. Trough spirometry (-45 min and -15 min assessments) should be done within 24 hours for once daily inhaled background therapy such as LABA/LAMA or LABA/ICS or LABA/LAMA/ICS from dosing on the previous morning and approximately 12 hours for twice daily LABA/LAMA or LABA/ICS or LABA/LAMA or LABA/ICS or LABA/LAMA/ICS from dosing on the previous evening. Otherwise, postpone visit to the next day where washout criteria can be fulfilled
Rescue medication only	Short-Acting Beta-2 Agonists (SABA)	Hold treatment at least 6 hours prior to each FEV 1 /spirometry measurement	If possible, postpone spirometry measurement on the same day until the washout criterion is fulfilled. Trough spirometry (-45 min and -15 min assessments) should be done within 6 hours after last rescue medication intake
Antibiotics for treatment of exacerbations and macrolides as background medication	Antibiotics, e.g. amoxicillin Macrolides, e.g. erythromycin	Systemic and/or inhaled antibiotics are allowed for treatment of acute infections, or are allowed for the treatment of acute exacerbations.	All data will be set to missing during the exacerbation time(time of SoC intake) and for 14 days thereafter with the exception of macrolides for those

Rationale/Group	Medication	Prohibition Period	Action Taken

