#### 8.4.4 COPD Exacerbation

Symptom-defined COPD exacerbations identified by the EXACT-PRO instrument (EXACT-PRO-defined exacerbations) are defined as a persistent increase from baseline in total EXACT-PRO score of ≥9 points for 3 days or ≥12 points for 2 days. Whenever the EXACT-PRO diary data suggest that the subject symptoms are worsening according to the above definitions, the diary will trigger an alert advising the subject to contact the site.

A healthcare resource utilization (HCRU)-defined exacerbation is defined as an acute worsening of respiratory symptoms (consisting of at least two of the following symptoms: dyspnea, cough, sputum volume, sputum purulence, chest tightness or wheeze) that requires a change in treatment. HCRU exacerbations are defined as moderate if leading to treatment with systemic glucocorticosteroids and/or antibiotics, and as severe if leading to hospital admission or emergency room (ER) visit lasting >24 h in addition to treatment with systemic glucocorticosteroids and/or antibiotics. Mild HCRU exacerbations are events that can be managed with an increase in usual medication and without the addition of systemic therapy.

Exacerbation therapy is at the discretion of investigators. Suggested therapy includes 5 days of oral prednisolone (or equivalent) 40 mg/day and/or an oral 7 day course of amoxicillin 500 mg t.i.d. (alternatively amoxicillin/clavulanic acid 625 mg t.i.d. or clarithromycin 500 mg b.i.d.) (GOLD 2018).

Subjects who develop a COPD exacerbation between screening and prior to treatment will be screen failed but will be permitted to be re-screened after a minimum of 2 weeks after exacerbation SOC therapy has been stopped. (see Section 5). Scheduled spirometry should not be performed during an exacerbation until it has completely resolved, therefore any scheduled visits that include spirometric assessment should be postponed until the subject has recovered. Visits that do not include spirometric assessment can go ahead as planned. Of note, budesonide and fluticasone are sensitive substrates of CYP3A. Where administered systemically for a COPD exacerbation, efficacy and safety of these drugs should be carefully monitored (see also Section 6.2 for further details).

In case of exacerbation alerts, subjects will need to visit the Site as soon as reasonably possible and be assessed to confirm the exacerbation. This visit will be considered as an unscheduled visit.

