# **Commercially Confidential Information**

Subjects experiencing a moderate exacerbation during the treatment period will continue with their study treatment along with the standard of care (SOC) therapy for exacerbation (i.e. antibiotics and/or systemic corticosteroids). In case subjects are treated with antibiotics for their moderate exacerbation, subjects will have to come back to the site for another unscheduled visit approximately 2 weeks after last intake of their antibiotics, as a follow-up visit to provide sputum and blood samples. If the follow-up visit occurs within approximately 1 week from the next study visit, subjects can come back directly to the planned visit as per Assessment schedule and proceed with the respective procedures as per protocol for this study visit day.

Subjects experiencing a severe exacerbation who need to be treated in the hospital will be discontinued of study treatment during this time, with the possibility to restart study treatment approximately 2 weeks after the last day of their antibiotics intake for their exacerbation. Those subjects who took antibiotics should also provide sputum and blood samples before restart with study treatment. Subjects who were not treated with antibiotics during their hospital stay can restart with study drug directly after hospital stay.

Exacerbation start time is considered as the day the subject is provided with antibiotics or systemic corticosteroids. Exacerbation end date is considered as the day after the last intake of antibiotics or systemic corticosteroids. In case of intake of both antibiotics and systemic corticosteroids, start and end date of the exacerbation refers to the start and end date of the antibiotics intake.

Finally, if an exacerbation happens after EOS visit, subjects will be treated at the discretion of the subject's physician.

Following treatment for the exacerbation, the subject will be expected to continue in the study provided the investigator considers that the subject can safely return to their pre-exacerbation medications.

All HCRU-defined exacerbation events and given therapy should be recorded on relevant eCRF pages.

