6.1.1 Variables

The primary estimand, defined below, quantifies a hypothetical effect of 12 weeks treatment that would have been observed if all subjects remained on their treatment for 12 weeks:

- **Target population:** subjects with moderate to severe COPD with features of chronic bronchitis and a history of exacerbations and treated with any of the combinations of LABA, LAMA, or ICS LABA/LAMA, LABA/ICS or LABA/LAMA/ICS along with or without macrolides as background therapy.
- Variables of interest: change from baseline in fibrinogen after 12 weeks of treatment.
- Intercurrent events of interest:
 - 1. Discontinuation of study treatment or study participation before 12 weeks of treatment
 - 2. Intake of antibiotics to treat exacerbations (other than macrolides taken as background medication)
 - 3. Intake of systemic corticosteroids to treat exacerbations.
 - 4. Use of rescue medications before 12 weeks of treatment with study drug or placebo is complete
- **Summary measure:** mean difference between treatment groups (QBW251 compared with placebo).

Novartis	Confidential	Page 12 of 20
SAP Amendment 1		Study No. CQBW251B2202

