6.1.3 Statistical model, assumptions and hypotheses

The primary analysis will include all available data from subjects in the PD analysis set.

The fibrinogen samples taken within 2 weeks after exacerbation or during or after last dose of antibiotics other than chronically administered macrolide would be set to missing if a valid unscheduled assessment did not happen at that time point for the primary analysis.

The primary analysis will be performed using a one-sided test at alpha=0.1 (two-sided 80% confidence intervals) and estimated treatment difference (QBW251-Placebo) at week 12 will be reported along with the associated 80% confidence intervals.

The comparison of QBW251 to placebo will be evaluated by testing the following null hypothesis (H_0) versus the alternative hypothesis (H_1) :

H₀: There is no reduction in fibrinogen from baseline after 12 weeks of treatment in

QBW251 compared to placebo.

H1: There is a reduction in fibrinogen from baseline after 12 weeks of treatment in favor

QBW251 compared to placebo.

The change from baseline in fibrinogen data is assumed to be normally distributed. A MMRM will be fitted to the changes from baseline in fibrinogen for all time points until Day 84 visit including the fixed factors and covariates but are not limited to the following:

- Treatment group
- Visit/Time
- Treatment group by time interaction
- Smoking status
- Baseline fibrinogen value by time interaction.

If normality assumptions are not met, then the fibrinogen data may be log transformed.

Sensitivity analyses:

Novartis	Confidential	Page 13 of 20
SAP Amendment 1		Study No. CQBW251B2202

Supportive analyses:

Supportive analyses will be performed on subjects whose fibrinogen levels or bacterial load collected at the visits during the study based on the different baseline treatments like LABA, LAMA, or ICS using repeated measures model similar to primary analyses.

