The total frequency of COPD exacerbations over the 12-week treatment period will be analyzed using a generalized linear model assuming a negative binomial distribution.

The time at risk for a subject is defined as the length of time the subject is on treatment and the log (length of time) will be used as the offset variable in the model. The model will include treatment, antibiotic use, and the number of exacerbations in the past 12 months prior to screening as categorical variables. An estimate of the rate ratio together with 80% confidence intervals and corresponding p-value will be presented.

3. The percentage of subjects experiencing at least a COPD exacerbation

The proportion of subjects with at least one COPD exacerbation will be analyzed using logistic regression. The model will include treatment, antibiotic use, and the number of exacerbations in the past 12 months prior to screening as categorical variables. The estimated odds ratios will be displayed along with the associated 80% confidence intervals.

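### The exacerbation rate and proportion models adjust for antibiotic use with no time window; if it is coded as use during the study, a real reduction in the exacerbation rate is understated

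*SAP*

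**What the plan says.** SAP 6.3, items 2 and 3, specifies a negative binomial model for "The total frequency of COPD exacerbations over the 12-week treatment period" and a logistic model for having at least one exacerbation. Both carry the sentence "The model will include treatment, antibiotic use, and the number of exacerbations in the past 12 months prior to screening as categorical variables". Protocol 12.5.4 uses the same words for both models. The only date in that sentence belongs to the count of past exacerbations.

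Other places that bear on the meaning of the term:

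- SAP 6.1.1 lists as an intercurrent event "Intake of antibiotics to treat exacerbations (other than macrolides taken as background medication").
- SAP 6.1.3 sets fibrinogen samples to missing around "antibiotics other than chronically administered macrolide".
- Protocol Table 6-2 has one row headed "Antibiotics for treatment of exacerbations and macrolides as background medication".
- Protocol 8.4.4 has subjects with a moderate exacerbation continue study treatment along with "the standard of care (SOC) therapy for exacerbation (i.e. antibiotics and/or systemic corticosteroids"), and says that "Exacerbation therapy is at the discretion of investigators".
- Antibiotic use is not a stratification factor (protocol 6.3.2, smoking status only), and it is not among the baseline characteristics listed in SAP 7.2.
- The annualized rate is defined by EXACT-PRO (protocol Table 2-1, SAP Table 1-1), that is, by a sustained rise in the diary score (protocol 8.4.4).

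**The concern.** A covariate in a randomised comparison should be fixed before treatment starts. Antibiotics taken during the study often come after an exacerbation and because of it. A flag for any such use marks subjects who have had events, and it marks more of them in the arm with more events. Comparing arms within levels of the flag removes part of the difference that the model is meant to estimate.

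The text does not say which use is meant. It allows coding of use during the study, and that is a likely reading: the term is undated beside a dated one, it is not a listed baseline characteristic, and where background macrolides are meant elsewhere they are named. At stake are two named secondary endpoints, each reported as a ratio with an 80% confidence interval and, for the rate, a p-value.

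**Working it through.** **The plan's own figures.** The documents show no exacerbation rate, dispersion, antibiotic share or power for these models, and the sample size section is blacked out. The only size figure visible is about 100 randomised with 15% drop-out: 100 × 0.85 = 85, which agrees with the stated 84 or so. Everything below is illustrative.

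**Assumptions (not in the documents).** Placebo rate 1.5 per year, negative binomial dispersion k = 0.7, 84 days of follow-up for everyone, true rate ratio 0.60. Each event leads to antibiotics with probability p, the same in both arms. A share q of subjects takes antibiotics for other reasons. The flag is any antibiotic use during the study.

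**Set-up.** The mean count is μ = rate × 84/365.25, so 0.345 on placebo and 0.60 × 0.345 = 0.207 on drug. The probability of no antibiotic given y events is (1−p)^y × (1−q). The probability of any event is 1 − (1 + kμ)^(−1/k), which gives 0.266 and 0.176. The unadjusted odds ratio is (0.176/0.824)/(0.266/0.734) = 0.59. Without the antibiotic term the rate model returns 0.60 exactly.

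**One case by hand: p = 70%, q = 5%.** With s = 1−p = 0.3:

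- Unflagged share = 0.95 × (1 + kμ × 0.7)^(−1/k): placebo 0.760, drug 0.828.
- Mean count among the unflagged = sμ/(1 + kμ × 0.7): 0.0885 and 0.0564, ratio 0.64.
- Events among the flagged: 0.345 − 0.760 × 0.0885 = 0.278, and 0.207 − 0.828 × 0.0564 = 0.160.
- Mean count among the flagged: 0.278/0.240 = 1.16 and 0.160/0.172 = 0.93, ratio 0.80.

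Both within-flag ratios lie above 0.60. The fitted common ratio is 0.76, closer to the flagged value because most events fall there.

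**All cases, true rate ratio 0.60, equal prescribing** (negative binomial and logistic models fitted to the exact cell probabilities):

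| Events treated | Rate ratio, 5% other use | Odds ratio, 5% | Rate ratio, 20% other use | Odds ratio, 20% |
|---|---|---|---|---|
| 10% | 0.61 | 0.59 | 0.60 | 0.59 |
| 20% | 0.63 | 0.60 | 0.61 | 0.59 |
| 30% | 0.66 | 0.60 | 0.62 | 0.59 |
| 50% | 0.71 | 0.61 | 0.65 | 0.60 |
| 70% | 0.76 | 0.61 | 0.68 | 0.60 |
| 90% | 0.81 | 0.60 | 0.71 | 0.59 |

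**Checks.**

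- With a true ratio of 1.0 and equal prescribing, both ratios stay at 1.00 in every row.
- At 2.5 events per year and 5% other use, 30% to 90% treated gives 0.67 to 0.81.
- At 70% treated, 5% other use and 1.5 per year, dispersion from 0.3 to 1.5 gives 0.77 to 0.76.
- A separate simulation that also included a prior-exacerbation category, with 1 to 3 events per year and 50% or 80% treated, turned a true 0.70 into 0.79 to 0.84.
- Coded as baseline macrolide use (15% of subjects, with 1.5 times the rate), the estimate was 0.604 with and without the term.

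**Precision of the logistic model.** In simulated trials of 50 per arm (1.5 per year, ratio 0.60, 5% other use), the median standard error of the log odds ratio rises from 0.50 without the term to 0.63, 0.75 and 0.94 with 50%, 70% and 90% of events treated. SAP 1.4 says the trial was stopped early but gives no number analysed; a smaller number makes this worse.

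**The case against.** The strongest reply is that this is an ambiguity and the intended meaning may be harmless. The term stands beside a pre-screening covariate. An exception for macrolides, as in "antibiotics other than chronically administered macrolide", makes sense only if macrolides count as antibiotics, and Table 6-2 puts both in one row. The bacterial-load rule in SAP 6.2.1 says antibiotics with no macrolide exception. Usage is therefore not consistent enough to settle the reading. This stands. A reader might infer that anyone who programs the sentence literally will report a biased rate ratio. The documents do not support that, because the literal text fixes no window.

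Second, the events are EXACT-PRO-defined. A diary alert leads to a visit to confirm the exacerbation, and not every diary event need end in antibiotics. The treated share may be low, and at 10% to 20% the shift is small. Other use may also exceed 5%, because a flag for any antibiotic would take in acute infections and background macrolide users; protocol 4.1.1 expects 20% to 40% of subjects to have bronchiectasis. Both points stand and are why the ranges above are wide.

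Third, a reader might infer that the model could show benefit or harm where there is none. That needs prescribing per event to differ by arm. At 80% on placebo against 60% on drug, a true 1.0 would become a rate ratio of 1.15 and an odds ratio of 1.48 with 5% other use, or 1.08 and 1.15 with 20%. The drug is meant to be "efficacious with regards to reducing lung and systemic inflammation and bacterial colonization", and treatment is discretionary, so a difference is conceivable. But investigators are blinded (protocol 6.4) and nothing in the documents shows one. It remains hypothetical.

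Finally, these analyses are exploratory in tone and without multiplicity control. The Cox model in item 1 of SAP 6.3 has no antibiotic term, though it runs only if there are enough events. This limits the severity but does not justify leaving the covariate undefined.

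**Conclusion.** The point holds as a conditional one. Both documents leave the window of the antibiotic term open, and the open text permits a coding that adjusts for a consequence of many of the events. Under that coding and equal prescribing, a true rate reduction is understated: 0.60 becomes about 0.61 to 0.81 with 5% other use and about 0.60 to 0.71 with 20%, at 1.5 events per year and dispersion 0.7. There is no bias under the null, and for the odds ratio the cost is precision. Under baseline coding there is no problem.

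The sizes rest on assumed rates and shares, and the share of EXACT-PRO events treated with antibiotics is unknown. The protocol calls the study non-confirmatory (section 12). The fibrinogen model does not list the term, so a reader should not carry this point over to the primary result. A reader might also see an error in how item 2 sets events over the treatment period against an offset of time on treatment. The wording already points to on-treatment counting, so that is at most a clarification.

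**What to change.** Before unblinding, in SAP 6.3 items 2 and 3, replace the antibiotic term with *background macrolide use at baseline (yes/no)*. Drop the term if too few subjects use macrolides for the model to fit. Align protocol 12.5.4 if the protocol is amended for another reason.

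The cost is a short wording change. No new data are needed: background therapy is recorded on the eCRF (protocol 6.1.2) and stable macrolide use is checked at eligibility (protocol 5.1, criterion 6). The downside is at most a small loss of adjustment. If baseline macrolides were always meant, the change only clarifies.

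Optionally, add one sentence to item 2 saying that only events starting on treatment are counted, over the same days as the offset.

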#### 6.3.2 Treatment assignment, randomization

Upon signing the informed consent form, the subject will be assigned the next sequential number by the investigator. The investigator or his/her staff will contact IRT and provide the requested identifying information for the subject to register them into the Interactive Response Technology (IRT).

At Day 1, all eligible subjects will be randomized via IRT to one of the treatment arms. Randomization will be stratified by smoking status (current or ex-smoker).

The investigator or his/her delegate will contact IRT after confirming that the subject fulfills all the inclusion/exclusion criteria. IRT will assign a randomization number to the subject, which will be used to link the subject to a treatment arm and will specify a unique medication number for the first package of investigational treatment to be dispensed to the subject. The randomization number will not be communicated to the site personnel, but will be used by the IRT system. The subject will retain the subject number throughout the study as their unique identifier. If the subject fails to be treated for any reason, the IRT should be notified within 2 days that the subject was not treated, and the reason will be entered into the eCRF.

The randomization numbers will be generated using the following procedure to ensure that treatment assignment is unbiased and concealed from subjects and investigator staff. A subject randomization list will be produced by the IRT provider using a validated system that automates the random assignment of subject numbers to randomization numbers. These randomization numbers are linked to the different treatment arms, which in turn are linked to medication numbers. A separate medication list will be produced by or under the responsibility of Novartis Global Clinical Supply (GCS) using a validated system that automates the random assignment of medication numbers to packs containing the study treatment.

The randomization scheme for subjects will be reviewed and approved by a member of the Randomization Office.

Follow the details outlined in the Site Operations Manual regarding the process and timing of treatment assignment and randomization of subjects.

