1.4 Study design and treatment

This is a randomized, subject and investigator blinded, parallel-group, placebo-controlled study investigating the mode of action (MoA) and preliminary efficacy and safety of QBW251 administered orally twice daily (b.i.d.) for 12 weeks in subjects with moderate to very severe COPD (GOLD 2-4). Approximately 100 subjects will be randomized in a 1:1 ratio to either QBW251 or placebo. Based on the assumption of a 15% drop-out rate (% drop out based on completed proof-of-concept COPD study CQBW251X2201), it is expected to have approximately 84 subjects to complete the study. Interim analysis plans were discontinued with strategic decision to stop this trial prior to completion.

The study consists of the following periods (Figure 1-1) : Screening, Baseline / Day 1, Treatment, and End of the Study followed by an additional post-treatment safety phone call. The total duration for each subject in the study is up to approximately 19 weeks.

Figure 1-1 Study design

Commercially Confidential Information

Therefore, CQBW251B2202 study drug dose arms are:

- QBW251 CCI
- Placebo b.i.d

2 First interpretable results (FIR)

First interpretable results (FIR) will be provided for this trial. Commercially Confidential Information

3 Interim analyses

Commercially Confidential Information

4 Statistical methods: Analysis sets

For all analysis sets, subjects will be analyzed according to the study treatment(s) received.

No screen failure data will be presented.

The safety analysis set will include all subjects that received any study drug.

The pharmacokinetic (PK) analysis set will include all subjects with at least one available valid (i.e. not flagged for exclusion) PK concentration measurement, who received QBW251 and experienced no protocol deviations with relevant impact on PK data.

The pharmacodynamic (PD) analysis set will include all subjects with PD data at both baseline and at least one post-baseline assessment which are not affected by any protocol deviations.

The analysis sets and protocol deviation codes are related as follows:

Table 4-1		
Category Text description of deviation Deviation code		Data exclusion
Subjects are PDs:	e excluded from Safety analysis in case of these	Exclude subject from Safety analysis set
INCL01	Informed consent was not obtained before any assessment	Y

 Table 4-1
 Protocol deviation codes and analysis sets

Novartis	Confidential	Page 10 of 20
SAP Amendment 1		Study No. CQBW251B2202

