6.3 Statistical model, assumptions and hypotheses

The secondary objective analysis will include all available data from subjects in the PD analysis set.

The change from baseline in the logarithm of the total number of colony forming units including all different micro-organisms (\log_{10} CFU) and change from baseline in the secondary efficacy including global air trapping and spirometry parameter will be analyzed using the same model (MMRM) as for the primary variable of interest. Contrasts for treatment differences will be provided together with two-sided 80% Confidence Intervals.

Similarly, other secondary pharmacodynamics and efficacy endpoints (CASA-Q, SGRQ, CAT, EQ-5d-3L and EXACT-PRO) will be analyzed using the same model (MMRM) as for the primary variable of interest.

The following analyses will be performed to explore any differences in the exacerbation events that occur in QBW251 vs placebo:

1. Time to first exacerbation

The time-to-event analyses will be carried out only upon sufficient number of exacerbation events occur during the study to estimate the median in either of the treatment groups.

The time to the first on-treatment exacerbation (event) is defined as the start date of first exacerbation minus the date of randomization +1. Subjects who do not experience an exacerbation or discontinued earlier without an exacerbation will be censored for analyses purposes.

Novartis	Confidential	Page 15 of 20
SAP Amendment 1		Study No. CQBW251B2202

The hazard ratios for QBW251 compared with placebo and their corresponding 80% confidence intervals will be computed using Kaplan-Meier method. The stratification factor may include number of exacerbations in the last 12 months as ≤ 1 and ≥ 1 .

The Kaplan-Meier estimates of the survival functions for each treatment will be plotted.

A Cox proportional hazards regression model will be applied in time-to-event analyses to test the null-hypothesis H0: λ QBW251(t) / λ Placebo(t) = 1, where λ (t) is the hazard function for the failure time of subjects treated with QBW251 dose and Placebo, respectively.

The Cox regression model will be stratified by number of exacerbations in the last 12 months. The SAS procedure PROC PHREG will be used for analysis. Results will be presented with adjusted hazard ratios for treatment group comparisons and associated 80% confidence intervals. No check for the validity of proportional hazards assumptions will be done.

2. Annualized rate of COPD exacerbations

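### The exacerbation proportion is modelled without regard to observation time, and all three exacerbation models omit the randomisation stratum: two minor gaps that are cheap to close

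*SAP*

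**What the plan says.** SAP 6.3 lists three exacerbation analyses, which treat follow-up differently.

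- **Item 1, time to first exacerbation:** "Subjects who do not experience an exacerbation or discontinued earlier without an exacerbation will be censored for analyses purposes". The analysis is run only if there are enough events to estimate a median in either arm. For the Cox model, "The Cox regression model will be stratified by number of exacerbations in the last 12 months".
- **Item 2, annualised rate:** a negative binomial model in which "the log (length of time) will be used as the offset variable in the model". The time is time on treatment.
- **Item 3, proportion:** "The proportion of subjects with at least one COPD exacerbation will be analyzed using logistic regression". No offset, observation window or rule for event-free early leavers is given. Protocol 12.5.4 item 3 reads the same.

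Items 2 and 3 share one covariate list: "The model will include treatment, antibiotic use, and the number of exacerbations in the past 12 months prior to screening as categorical variables". Smoking status is not in it, nor in the Cox specification.

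On the design, Protocol 6.3.2 says: "Randomization will be stratified by smoking status (current or ex-smoker". It is the only stratum. The primary MMRM in SAP 6.1.3 has "Smoking status" among its terms. SAP 1.4 states that "Approximately 100 subjects will be randomized in a 1:1 ratio to either QBW251 or placebo", assumes 15% drop-out, expects about 84 completers and records a strategic decision to stop the trial early.

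**The concern.** In a plain logistic model, a subject who leaves event-free counts the same as one observed event-free for all 12 weeks. The fitted percentage is then the chance of being seen to have an event while observed, which is lower than the 12-week risk. If one arm is observed for less time, it shows fewer events for that reason alone.

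Item 3 could matter more than its place in the list suggests. If fewer than about half the subjects have an event, the median is not estimable and item 1 may not be run. The crude proportion would then be the only reported risk of a first exacerbation, with no follow-up-adjusted counterpart. The item 2 rate model would still run, but it estimates a rate.

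The smoking omission is a separate matter. An analysis would normally carry the stratification factor, the primary model does so, and no reason is given for dropping it here.

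**Working it through.** **The plan's own figure.** 100 × (1 − 0.15) = 85 completers against about 84 stated; 84 / 0.85 = 98.8, so 99 against about 100 randomised. These agree within rounding. No exacerbation rate or by-arm drop-out is visible, so everything below rests on assumed values.

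**Effect on the percentage and odds ratio (OR).** Assume a 12-week risk of 40% in both arms (no effect), constant hazards, and drop-out that ends observation. Let H = −ln(0.60) = 0.5108 and D = −ln(1 − drop-out). Then

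crude proportion = H/(H + D) × (1 − exp(−(H + D))).

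- 15% drop-out: 0.7586 × 0.49 = 37.2%. If both arms have 15%, OR = 1.00.
- 20%: 0.6960 × 0.52 = 36.2%. 10%: 0.8290 × 0.46 = 38.1%. OR = (0.362/0.638)/(0.381/0.619) = 0.92.
- 30% v 5%, an extreme chosen for scale: 34.2% v 39.1%, OR 0.81.

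**Restricted to subjects followed past Day 28.** Day 28 is one third of 84 days, so

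proportion = (1 − 0.6^(1/3)) + 0.6^(1/3) × H/(H + D) × (1 − exp(−(2/3)(H + D))).

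- 20%: 0.1566 + 0.8434 × 0.6960 × 0.3869 = 38.4%. 10%: 0.1566 + 0.8434 × 0.8290 × 0.3369 = 39.2%. OR 0.97.
- 30% v 5%: 37.5% v 39.6%, OR 0.91.

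**Early stop.** If a share f = 30% (assumed) is cut off uniformly over the 12 weeks, the proportion is 0.70 × 0.40 + 0.30 × (1 − 0.40/0.5108) = 0.280 + 0.065 = 34.5%. If this applies equally to both arms, the null OR stays at 1.00.

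**Sensitivity to the assumptions.** With event rates of 1 to 4 per subject-year and drop-outs leaving uniformly:

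- 20% on QBW251 v 10% on placebo gives null ORs of 0.94 to 0.90. The reverse split gives 1.07 to 1.11.
- With a true rate ratio of 0.7 and 15% drop-out in both arms, the OR moves only 0.5 to 3% towards 1.

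A simulation used 100 subjects, 1,500 runs, 2 events per subject-year and 25% v 5% drop-out. Plain logistic regression gave OR 0.85 and 16% one-sided rejection at nominal 10%. A complementary log-log model with a log(follow-up) offset gave a ratio of 1.02 and 9%. Adding smoking status to the logistic model did not help (0.85 and 17%).

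**Scale.** At 50 per arm and 40% risk, the 80% interval for the OR extends by a factor of exp(1.2816 × √(2/(50 × 0.40 × 0.60))) = 1.69 each way. A bias to 0.92 is 0.083 on the log scale against a half-width of 0.523, about one sixth.

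**Smoking status.** Assume two equal strata, balanced across arms, with overall control risk 40% and conditional treatment OR 0.50. Averaging over strata gives a marginal OR of 0.51 if smoking has OR 2 and 0.53 if it has OR 4, an attenuation of 2.5 to 9.5% on the log scale. With no treatment effect the marginal OR is 1.00. In simulation (smoking rate ratio 2, equal drop-out), one-sided rejection at nominal 10% was 8.1% without smoking and 8.6% with it.

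**The case against.** Much of the case against a stronger claim stands.

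- **Early leavers.** A reader might infer that someone who leaves in week 2 is scored as a 12-week non-event. SAP 6.3 uses the PD analysis set, which requires a post-baseline PD assessment (SAP 4). After Day 1 the first site visit is Day 28; Day 14 is a telephone call. The early-termination column of Protocol Table 8-1 shows no fibrinogen draw. Such a subject would normally drop out of the set, unless daily EXACT-PRO entries count as PD data, which the plan does not say. This is why 0.97 stands beside 0.92.
- **Stopping treatment is not leaving the study.** Protocol 9.1.1 keeps subjects who stop treatment under assessment where possible. The calculation treats all drop-out as lost observation.
- **Unequal drop-out is not documented.** Only the overall 15% is given. There is an arm-specific route: Protocol 9.1.1 ends treatment on exposure thresholds, and Protocol 8.5.2 evaluates PK samples only in subjects given QBW251. The documents do not size it, and it shortens observation only if item 3 counts on-treatment time.
- **The early stop** is administrative and the trial is 1:1 and blinded, so it should affect both arms alike. The documents do not say how many subjects it cut short, so incomplete follow-up is likely, not certain.
- **Companion analyses** already use follow-up time. This answers part of the point, but item 1 is conditional on events and item 2 does not give a risk.
- **Smoking** is balanced by the stratified randomisation, so omitting it does not bias the test under no effect. With sparse events, adding it as a further Cox stratum could cost something; a covariate avoids that.

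**Conclusion.** Both textual points hold, and both are minor. The item 3 percentage will probably understate the 12-week risk, by about 3 points at 15% drop-out if the true risk is 40%. The odds ratio is biased only if observation time differs by arm. For an assumed 10-point difference in drop-out with no true effect, it would be 0.92, or about 0.97 under the Day 28 restriction, against an 80% interval spanning a factor of about 1.7 each way. Risk, drop-out split and constant hazards are all assumptions.

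Omitting smoking status attenuates a conditional odds ratio of 0.50 to about 0.51-0.53 and is inconsistent with the design and the primary model.

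A reader might go further and infer that the exacerbation comparison is biased in favour of QBW251, or that leaving out the stratum distorts the treatment estimate under no effect. The documents support neither: they give no by-arm follow-up, and the stratum is balanced by design. The analyses are described as exploring differences, use 80% intervals, have no multiplicity adjustment and concern a secondary endpoint. No primary or key secondary conclusion depends on them.

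**What to change.** 1. **Item 3.** Report the Kaplan-Meier Day 84 risk per arm with an 80% confidence interval for the difference, whether or not the median is estimable. Alternatively, use a binary model with complementary log-log link and log(days observed) as offset, which comes close to re-estimating the item 1 hazard ratio. Either way, define the observation window, and keep the crude proportion as a descriptive figure. Both options assume that leaving is unrelated to exacerbation risk given the model.
2. **All three models.** Add smoking status as a covariate in the negative binomial, logistic and Cox models. In the Cox model use a covariate, not a further stratum, because events may be sparse.

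The cost is SAP wording, a few lines of code and one extra parameter per model.
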